4.2 Exclusion Criteria

4.2.1 BMI $< 18.5 \text{ Kg/m}^2$.

4.2.2 Previous treatment for breast cancer including chemotherapy, endocrine therapy and radiotherapy. Women with prior DCIS who were treated with surgery only and whose treatment ended ≥ 2 years prior to enrollment are eligible for the trial.

4.2.3 Women who are planned to receive neoadjuvant therapy.

4.2.4 Participants may not be receiving investigational agents.

4.2.5 History of allergic reactions attributed to compounds of similar chemical or biologic composition to exemestane.

4.2.6 Uncontrolled intercurrent illness including, but not limited to, ongoing or active infection, symptomatic congestive heart failure, unstable angina pectoris, cardiac arrhythmia, or psychiatric illness/social situations that would limit compliance with study requirements.

4.2.7 Other co-existing invasive malignancies (with the exclusion of basal cell carcinoma or skin squamous cell carcinoma) diagnosed during the last 2 years before randomization.

- 4.2.8 History of severe osteoporosis (T score \leq -4 either spine or hip), or presence of vertebral fracture.
- 4.2.9 Use of systemic Hormone Replacement Therapy (HRT) in the last 30 days prior to the randomization. The use of non-systemic estrogen (such as vaginal estrogen use) is allowed.
- 4.2.10 Use of any chemopreventive agents (SERM) in the last 3 months.
- 4.2.11 Concomitant use of CYP3A4 inducer medication (rifampicin, phenytoin, carbamazepine, phenobarbital, and St. John's wort).

4.3 Inclusion of Women and Minorities

Participants will be adult women of all races and ethnic groups. Breast cancer is extremely rare in men and men have limited amounts of normal breast tissue; therefore, male participants will not be recruited to this trial. Children will not be recruited to the trial because breast cancer is not relevant to the child population. Every attempt will be made to recruit minority women at the Italian sites. However, given that the distribution of the Italian population mainly consists of white Caucasians (about 93%), we expect very few participants of different ethnic background to be enrolled at the Italian sites. At the US sites efforts will be made to enroll women from a diversity of ethnic and socio-economic backgrounds.

4.4 Recruitment and Retention Plan

This multicenter protocol will be conducted at the following five sites: the European Institute of Oncology (IEO), Milan, Italy; the E.O. Galliera, Genoa, Italy; the Columbia University Medical Center (CUMC), New York, NY; the UT MD Anderson Cancer Center, Houston, TX; and the Moffitt Cancer Center, University of South Florida, Tampa, FL. The IEO will be the Lead Site. The high rate of breast cancer surgeries at these sites will allow the recruitment of the required samples size. Efforts will be made to enroll women from a diversity of ethnic and socio-economic backgrounds. Recruitment and retention effort will be evaluated routinely by the site coordinator and the study staff. The study recruitment and retention plan will be modified as necessary to promote rapid accrual and to assure 100% recruitment rate of participants. Please refer to the study-specific recruitment and retention plan for more details.

5. AGENT ADMINISTRATION

Intervention will be distributed on an outpatient basis. Reported adverse events (AEs) and potential risks are described in Section 6.2.

5.1 Dose Regimen and Dose Groups

Arm 1

Agent: Exemestane

Doses: one dose of 25 mg once a day

Duration: 4 to 6 weeks

Arm 2

Agent: Exemestane

Dose: 25 mg three times a week

Duration: 4 to 6 weeks

Arm 3

Agent: Exemestane

Doses: 25 mg once a week

Duration: 4 to 6 weeks

5.2 Exemestane Administration

Investigational drug pharmacy will be responsible for drug distribution. [name] (PI) and the local Site Investigators or their designees will be responsible for drug administration. They can delegate to other study investigators (MDs and research nurses) to distribute the agent on their behalf.

Participants will receive a 6-week supply (2 wallets containing 3 blisters each) of the drug/placebo as outlined in the clinical procedure schema (see Section 7.1 for a detailed description). Each wallet will consist of 3 blisters, each blister for 7 days of treatment. Each blister will have 7 tablets numbered from 1 to 7 to clearly mark the order to be taken by the participants. Based on the arm, the blister will contain 7 active tablets 1 through 7, or three active tablets corresponding to days 1, 3 and 5 and four placebo tablets at days 2, 4, 6 and 7, or one active tablet placed at day 1 and 6 placebo in the remaining 6 days. The participant will be advised to take one tablet per day after dinner, always at approximately 8 PM, starting from day 1 till the night before surgery. If for any reason they will skip a tablet they will be instructed to leave it behind and take the one for the corresponding day. Participants will be asked to contact the study coordinator the first time they miss a dose.

5.3 Run-in Procedures

No run-in procedure will take place in the present protocol.

5.4 Contraindications

Eligible participants should not have specific contraindication to exemestane, considering also the short period of treatment. Any pre-existing musculoskeletal disorder should be carefully evaluated before enrolling the participants. Furthermore, medications that may impact participant safety or scientific integrity of the study are non-allowed, such as the following: strong CYP 3A4 inducers (*e.g.*, rifampicin, phenytoin, carbamazepine, phenobarbital, or St. John's wort).

5.5 Concomitant Medications

All medications (prescription and over-the-counter), vitamin and mineral supplements, and/or herbs taken by the participant will be documented on the concomitant medication CRF and will include: 1) start and stop date, dose and route of administration, and indication. Medications taken for a procedure (*e.g.*, biopsy) should also be included.

5.6 Dose Modification

Participants will be asked to maintain the full dose throughout the treatment period. Due to the short time of treatment no dose modification will be applied.

Toxicity will be evaluated using the NCI terminology criteria (CTCAE version 4.0.3, published 06/14/2010).

If grade 1 or 2 toxicity occurs, the participant will be maintained on treatment irrespective of attribution to

the study drug. In case of grade 3 toxicity unrelated or unlikely to be related to study treatment, participant may remain on treatment as per physician judgment, women who experience other grade 3 or more severe adverse events will be removed from the study.

Toxicity Grade	Attribution to study drug				
	Unrelated	Unlikely	Possible	Probable	Definite
1	C	C	C	C	C
2	C	C	C	C	C
3	C ¹	C ¹	W	W	W
4	W	W	W	W	W

C = Continue drug

C¹ = Continue drug as per physician judgment

W = Withdrawal

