3. SUMMARY OF STUDY PLAN

We will conduct a multicenter, pre-surgical double-blind non-inferiority phase IIb study in which participants will be randomized to receive either exemestane 25 mg/day or 25 mg/ three times a week or a single dose of 25 mg/week for a minimum of 4 up to 6 weeks.

A total of 180 post-menopausal women will be accrued; 60 per arm, enrolled in 35 months and treated for a minimum of 4 up to 6 weeks.

Participants will be histologically-confirmed ER-positive (ER $\geq 10\%$) primary breast cancer patients who are candidates for breast surgery. Postmenopausal women younger than 76 years of age with cT₀₋₂, cN₀₋₁, M_x or women with larger tumors who refuse neo-adjuvant therapy before surgery are eligible. No previous treatment for breast cancer is allowed.

Complete physical exam and safety lab tests will be performed at baseline and at end of treatment (28+1, 35+1, 42+1 days). Phone contact will occur at day 1 and a week before surgery (+3 days).

Biomarkers: blood samples will be collected at baseline and the end of treatment (fasting blood for biomarkers will be collected prior to randomization and either on the day of surgery or the day before; fasting is strongly recommended but is not mandated), tissue samples will be collected from the diagnostic or research biopsy and at the time of surgery.

Duration of study will be four years: 35 months for accrual, 4-6 weeks of treatment, and one year for biomarkers measurement.

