6.9 Blinding and Unblinding Methods

- Participants will be blinded to exemestane schedule.
- The Statistician and the Site Study Pharmacist will not be blinded to exemestane schedule.
- All other Investigators will be blinded to exemestane schedule.
- All participants will take 1 tablet per day.
- Study assignments will be unblinded to the Study Investigators and Site Coordinators after all of the data are collected and the study database has been locked. Unblinding will also occur if the participant's physician deems that unblinding is necessary, such as in the case of unacceptable toxicity thought to be related to the study agent or progressive disease.
- The Data and Safety Monitoring Board will also be blinded unless unblinding is warranted (if the participant's physician deems that unblinding is necessary, if the participant becomes pregnant, or after all of the data are collected and the study database has been locked).
- Unblinding will only take place after consultation with the NCI, DCP Task Order Monitor (Medical Monitor). Unblinding will be conducted as follows:

- 1) The Site Investigator contacts the Protocol Principal Investigator and requests the participant's treatment status be unblinded.
- 2) The Protocol Principal Investigator contacts the NCI, DCP Task Order Monitor (Medical Monitor) and requests the participant's treatment status be unblinded. The Protocol Principal Investigator then conveys the Task Order Monitor's decision to the Site Investigator. The Site Investigator then proceeds with unblinding as written out below.

- 3) If the NCI Task Order Monitor cannot be reached and the participant requires emergency care, the Protocol Principal Investigator may authorize the Site Investigator to break the blind.
- 4) If the Site Investigator is unable to reach the Protocol Principal Investigator and the participant requires emergency care, then the Site Investigator must proceed with unblinding as written out below.
- 5) The Site Investigator requests the participant's treatment status be unblinded by the research pharmacist (or designated individual responsible for dispensing drug).
- 6) The Site Investigator officially takes the participant off-study.
- 7) The date and reason for breaking the blind must be submitted by the Site Investigator to the Protocol Principal Investigator, [name], as soon as possible.

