7.5 Evaluation at Completion of Study Intervention

At the final visit, participants will undergo physical exam, vital signs, and anthropometric measurements (weight, waist measurement, hip measurement). These procedures may be done **within 7 days prior to surgery or on the day of surgery**. Do not repeat the height assessment at the Final Visit. Height measurement will be used from the baseline visit.

Blood tests for safety that do not require fasting may be done **within 7 days prior to surgery or on the day of surgery**:

- complete blood count (CBC), AST, ALT, Na, K, BUN, total bilirubin, Cl, Ca, alkaline phosphatase, and creatinine

All other procedures are performed the day of surgery or the day before surgery:

Fasting blood lab tests that are performed at the local lab (glucose, total cholesterol, HDL cholesterol and triglycerides). Fasting is strongly recommended, but is not mandated. Every effort should be taken to draw these labs fasting.

Fasting blood for biomarkers will be collected. Fasting is strongly recommended, but is not mandated. Every effort should be taken to draw these labs fasting.

The date and time of blood draw, the date and time of surgery, and the date and time of last pill intake will be recorded.

The use of concomitant medications, adverse events, compliance, and quality of life assessment will be assessed. Study agent will be collected. A review of agent diary will be performed.

Any kind of surgery will be allowed from simple lumpectomy to total mastectomy. Tissue samples will be collected from the surgical specimen and processed according to Section 10. A detailed Manual of Operations and Procedures will be implemented with the specific procedures for each specimen.

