8.3 Off-Agent Criteria

Participants may stop taking study agent for the following reasons: completed the protocol-prescribed intervention, adverse event or serious adverse event, inadequate agent supply, non-compliance, concomitant medications, medical contraindications. Participants will continue to be followed, if possible, for safety reasons and in order to collect endpoint data according to the schedule of events. Participants will not be replaced.

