8.4 Off-Study Criteria

Participants may go 'off-study' for the following reasons: the protocol intervention and any protocol-required follow-up period is completed, adverse event/serious adverse event, lost to follow-up, non-compliance, concomitant medication, medical contraindication, withdraw consent, death, determination of ineligibility (including screen failure).

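### Sections 5.6 and 6.9 send women off the study for toxicity or unblinding, although the intention-to-treat analysis needs their surgery-linked estradiol sample

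*Combined protocol and SAP*

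**What the plan says.** **Rules that end study participation.** Section 5.6 lets a woman with unrelated or unlikely-related grade 3 toxicity stay on treatment at the physician's discretion, then states that "women who experience other grade 3 or more severe adverse events will be removed from the study". By the table below it, that means grade 3 events at least possibly related to the drug and grade 4 events of any attribution. The table key sets continuing the drug against W, withdrawal, without saying from what. Section 6.9 allows unblinding "such as in the case of unacceptable toxicity thought to be related to the study agent or progressive disease". Step 6 of that procedure reads "The Site Investigator officially takes the participant off-study".

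**Rules that keep the woman in.** Section 8.3 lists an adverse event among the reasons for stopping the agent and continues: "Participants will continue to be followed, if possible, for safety reasons and in order to collect endpoint data". It adds: "Participants will not be replaced". Section 13.6 makes the primary analysis intention to treat regardless of compliance. Section 13.8 includes every randomized woman who received at least one dose.

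**Off-study reasons.** Section 8.4 says that participants may go off-study for an adverse event and also for "non-compliance, concomitant medication, medical contraindication, withdraw consent, death". It does not say how this relates to 8.3.

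**Sampling.** Section 3 states that "blood samples will be collected at baseline and the end of treatment". Section 7.5 lets the physical exam and safety bloods be done up to a week before surgery, but for the rest, including biomarker blood, "All other procedures are performed the day of surgery or the day before surgery".

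**The concern.** One event, a related adverse event that stops the drug, gets two instructions. Under 5.6 the woman leaves the study. Under 8.3 she stops tablets and is still sampled. The primary endpoint is percentage change in serum estradiol from baseline, and there is no intermediate sample to fall back on. If she leaves before the final draw, she has no endpoint value.

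Most of this loss is avoidable, because the participants are surgical candidates who can still be expected at the hospital. It is also not random, since related toxicity may depend on dose and women who stop early may be less suppressed at surgery. Section 13.6 tests whether missingness is associated with assigned treatment. That can reveal an imbalance but cannot recover the missing values, and no rule is given for a missing final estradiol.

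**Working it through.** **1. The rules side by side.**

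| Event | Rule ending participation | Rule keeping the woman in | Conflict |
|---|---|---|---|
| Related grade 3, or any grade 4 | 5.6: out of the study | 8.3: off agent, endpoint collected if possible; 13.6 and 13.8: analysed | Direct |
| Blind broken | 6.9 step 6: off-study | 8.3 does not list unblinding; 13.6 and 13.8: analysed | Through 13.6 and 13.8 only |
| Adverse event generally | 8.4: may go off-study | 8.3 | None in itself; 8.4 is permissive and can follow 8.3 in sequence |

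**2. The plan's own figure.** Inputs from section 13.4: margin 6 points, SD 11, true difference 0, one-sided alpha 0.025, 54 evaluable per arm.
- SE = 11 × √(2/54) = 2.117, with 106 degrees of freedom.
- Noncentrality = 6/2.117 = 2.83. Noncentral-t power = 80.2%, which agrees with the stated 80%.
- 162/0.9 = 180 randomized, as stated.

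**3. Illustration of keeping versus removing.** The documents give neither a removal rate nor the estradiol level of early stoppers. Assume that k of 60 women in the daily arm stop by this route and none in the comparator, and that each would show a reduction 20 or 40 points smaller than the other women in her arm. The true difference is 0 with these women included. The plan's 54 per arm is used throughout.
- Removed: the contrast shifts against the reduced schedule by (k/60) × gap. Noncentrality = (6 − shift)/2.117.
- Kept: no shift, but the daily-arm SD becomes √(11² + f(1−f) × gap²) with f = k/60. SE = √((SD² + 11²)/54).

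| k of 60 | Gap | Shift if removed | Daily-arm SD if kept | Power kept | Power removed |
|---|---|---|---|---|---|
| 1 | 20 | 0.33 | 11.3 | 79% | 76% |
| 3 | 40 | 2.00 | 14.0 | 69% | 47% |

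Worked for the second row:
- Shift = 0.05 × 40 = 2.00.
- SD = √(121 + 0.0475 × 1600) = √197 = 14.0.
- SE if kept = √((197 + 121)/54) = 2.43, so noncentrality = 6/2.43 = 2.47.
- Noncentrality if removed = 4/2.117 = 1.89.

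Three of 60 is half of the assumed 10% drop-out.

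**4. Direction.** Losing less-suppressed women from the daily arm makes the reference look better and works against non-inferiority. Losing them from a reduced-frequency arm works in its favour. Equal losses with equal gaps cancel. Section 2.3 expects lighter schedules to be better tolerated, which makes daily-arm losses the more plausible case, but nothing in the documents settles it.

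**The case against.** The best defence is that the text can be read coherently. Section 5.6 is about dose modification, its table contrasts continuing the drug with withdrawal, and 8.3 is the specific rule on endpoint collection after stopping. A careful site might do the right thing. But the prose of 5.6 says the study, in the same sentence that uses treatment for the milder case, so the reading is not secure.

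Other points stand and limit the concern:
- Section 8.3 is qualified by feasibility and does not mention unblinding. Section 13.8 does not itself demand a final sample; the need follows from intention-to-treat inclusion plus the endpoint definition.
- Not every loss is treatment-related. W covers unrelated grade 4 events, and 6.9 also names progressive disease.
- Numbers are probably small. Treatment lasts 4 to 6 weeks, section 2.3 reports an earlier presurgical trial of daily exemestane without significant toxicity, and unblinding outside emergencies needs the medical monitor.
- The 10% drop-out allowance covers the loss of numbers, though not bias.
- Section 13.4 includes time since last dose in the ANCOVA, which would absorb part of an early stopper's gap.

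A reader might infer that power falls from 80% to 47%. The documents do not support that. The gap has no source in them, and the right comparator is the trial with these women kept, whose wider spread already brings power to 69% in that extreme case. If instead the zero difference holds among the evaluable women, removal shifts nothing and power stays at 80.2%.

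A reader might also infer that the conflict biases the trial towards a false claim of non-inferiority. That needs losses concentrated in a reduced-frequency arm, which the documents do not indicate.

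**Conclusion.** The inconsistency is in the current text and should be corrected. Followed literally, 5.6 and 6.9 step 6 produce avoidable missing primary-endpoint data, some of it treatment-related, in an analysis meant to include every dosed woman.

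The size cannot be fixed from the documents. Under the assumptions shown (daily-arm losses only, gap of 20 to 40 points), removal rather than retention costs about 3 points of power with one woman lost and a 20-point gap, and about 22 points with three lost and a 40-point gap. These figures illustrate the mechanism and do not forecast the trial. The case for the change rests on the conflicting instructions and on how little it costs to remove them. Confidence is medium, because the number affected is unknown and probably small.

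**What to change.** - **5.6:** replace removal from the study with *taken off study agent*, define W as withdrawal of study agent, and refer to 8.3.
- **6.9 step 6:** replace off-study with *off-agent*, and refer to 8.3.
- **Both:** state that the final blood draw and surgical sample are still collected where possible and medically safe, unless the woman withdraws consent, is lost to follow-up or dies.
- **8.4 (optional):** add a matching sentence.

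The cost is amendment wording. The draw is already tied to surgery, so no visit is added, and the safety rules for stopping the agent stay as they are.

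There is one downside. Off-drug women kept in the daily arm add variance and can pull the contrast towards non-inferiority, so the compliant-only analysis in 13.6 should be read alongside the primary result.

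A separate minor point: 13.8 places drop-outs in a failure group, but a continuous percentage change has no failure value. That sentence should be limited to the binary below-detection comparison in 13.4 or to a sensitivity analysis.

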5.7 Adherence/Compliance

5.7.1

There is no “gold standard” yet on how to measure participant compliance. Recent data from ongoing chemoprevention studies have estimated compliance to be between 60% and 100%, and this disparity can be attributed to adherence methodology assessment.

Compliance estimates will be limited to pills that fall within the required dosing period (depending on total number of days between first dose and surgery). To be compliant, a participant has to take $\geq 80\%$ of the active scheduled pills overall and also specifically, $\geq 80\%$ compliant in the last 7 days before surgery. We propose the use of multiple methods of adherence monitoring: subject self-reporting, pill diary and tablets count. Drug and its metabolite will be also measured, but due to different schedules and the half-life of exemestane, these measurements may not be indicative of compliance for arms 2 and 3.

5.7.2

Pill diary completion: Each participant will receive a 42 days diary to facilitate tracking and recording of pill intake (Appendix B). Each participant will be asked to write Yes/No in the corresponding day of the diary and to register the time of drug intake. Participants are asked to fill the diary and some additional space will be left for participant’s notes. Participants will be asked to contact the study coordinator the first time they miss a dose. Each pill diary will be returned at the final scheduled visit. The amount of pills and the pill diary are for the total admitted period of treatment.

Dose count: Each participant will receive a 42 day supply of the drug / placebo and will be asked to return both wallets with full and empty blisters. Overall compliance will be measured by blinded staff as follows:

number of tablets taken (i.e., number of tablets given-number of tablets returned)/number of tablets that should have been taken during that period of time.

Any missed pill in each blister will be recorded in order to collect the compliance of active pills at a later stage (unblinded statistician).

In cases where the tablets are not returned, the compliance will be calculated only from the pill diary.

Drug/metabolite plasma levels: Circulating levels of exemestane and 17-dihydroxyexemestane will be

measured using LC-MS/MS technology.

